9.3.3.3 Analyses of categorical and ordinal variables

Binary variables include:

- Indicator of 30 day HF rehospitalization (after a prior in-study HF hospitalization);
- Responder for at least 5-point change in deterioration and responder for at least 5-point improvement for KCCQ scores. .

The 30-day HF rehospitalization will be analyzed using logistic regression with treatment and region as fixed-effect factors. For 30 day hospital readmission, the analysis set will be restricted to patients who had hospitalization for HF at least once during double blind period.

The responder analysis for KCCQ score changes from baseline (for both run-in epoch baseline and randomized epoch baseline) at various visits (defined separately for patients with at least 5 point deterioration and for patients with at least 5 point improvement) will be performed using a generalized mixed model with treatment, region, visit, and visit-by-treatment as fixed factors and baseline score as covariate, with a common compound symmetry covariance matrix among visits for each treatment group. Treatment effect size estimates and 95% CIs at various visits will be provided. The analysis will be performed based on all available data up to Year 3 in the FAS.

Ordinal variables include:

- Assessment in the clinical composite assessment (improved, unchanged, and worsened) at post-randomization visits;
- Change in NYHA class from randomization;
- Changes in HF signs and symptoms from randomization;
- Patient global assessment at 8 months.

The first three variables will be analyzed, at Month 8, 1 year, 2 years, and 3 years, using a repeated measures proportional cumulative odds model. The model will include patient as a random effect and the randomized treatment phase baseline category (only for NYHA class and HF signs and symptoms), region, treatment, visit (all available post-randomization visits) and treatment-by-visit interaction as fixed effect factors. This model assumes that the treatment effect sizes across measurement categories are the same. The visit-wise effect size estimates and their 95% confidence intervals will also be provided. The analysis will be based on all available data in the FAS and likelihood method with an assumption of missing at random for missing data. The patient global assessment at 8 months will be analyzed similarly but using a non-repeated measures proportional cumulative odds model. The SAS procedure of GLIMMIX ([SAS/STAT 9.3](#)) can be used for the analysis.

The clinical composite assessment at a selected visit is defined as:

- Improved, if i) NYHA class decreases at least one level and Global Assessment is not worse at the selected visit and there is no major AE up to the selected visit; or ii) Global

assessment is improved and NYHA class does not increase at the selected visit and there is no major AE up to the selected visit.

- Worsened, if i) NYHA class increases at the selected visit; or ii) Global Assessment is worse at the selected visit; or iii) experiences a major AE up to the selected visit.
- Unchanged, if neither “Improved” nor “Worsened”.

For Global Assessment, we converted the seven-category classification (recorded in the eCRF) to three-category classification in defining the clinical composite assessment:

- Markedly improved and Moderately improved to Improved;
- Moderately worsened and Markedly worsened to Worsened;
- Slightly improved, Unchanged, and Slightly worsened to Unchanged.

Major AEs are adjudication-confirmed CV death and heart failure hospitalizations.

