6.6.2 Health-related Quality of Life

HF symptoms reduction and reduction in physical limitation

The KCCQ is a self-administered questionnaire that requires 4-6 minutes to complete. It contains 23 items, covering physical function, clinical symptoms, social function, self-efficacy and knowledge, and Quality of Life (QoL).

The HF symptoms and physical limitation domains scores show the best correlation for improvements following a chronic heart failure (CHF) exacerbation ([Green et al 2000](#)). Thus, one of the secondary endpoints is a clinical summary score based on the HF symptoms and physical limitation domains scores of the KCCQ at 8 months. All other domains will be analyzed as exploratory endpoints.

The KCCQ is available in a number of validated translations. Patients in whose language a validated translation of the KCCQ is not available will be exempt from completing this instrument.

Clinical composite assessment

The clinical composite assessment is one of the exploratory endpoints of this study. It is derived from the patient global assessment and the NYHA class, combined with the occurrence of major adverse clinical events as defined by CV death and hospitalization for HF.

The patient global assessment is a seven-point patient self-evaluation scale. At Visit 201, the investigator should call the patient's attention to how he/she feels about his/her condition at that time and explain that periodically throughout the study the patient will be asked to rate how he/she feels compared to at the randomization visit (Visit 201). This evaluation is combined with the NYHA class, a reliable instrument for rating HF patients' functionality, and with major adverse clinical events as defined by CV death and hospitalization for HF to arrive at an overall evaluation of whether a patient is considered to have improved, worsened, or remain unchanged after a pre-specified period of time ([Packer 2001](#)).

Assessment of HF signs and symptoms/NYHA class will be conducted at all visits.

EuroQol (EQ-5D)

The EuroQol (EQ-5D) instrument assesses the current health status of patients. It consists of five domains and one visual analogue scale. This instrument assesses morbidity, self-care, usual activity, pain, and anxiety and depression of patients.

The EQ-5D is available in a number of validated translations. However, patients in whose language a validated translation of the EQ-5D is not available will be exempt from completing this questionnaire.

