Change from baseline to month 8 NYHA class will be analyzed using a repeated measures proportional cumulative odds model. The response variable is the category change from baseline to any given time points (4 weeks and 16 weeks) up to Month 8 (32 weeks) (expressed as improved, unchanged, worsened). The NYHA class change after patients who have died will be categorized into 'worsened'. The model will include patient as a random effect and the randomized treatment phase baseline NYHA class, region, treatment, visit and treatment-by-

visit interaction as fixed effect factors. This model assumes that the treatment effect sizes across measurement categories are the same. The analysis will be performed based on all available data up to 8 months in the FAS and based on likelihood method with an assumption of missing at random (MAR) for missing data not due to death. The estimated between treatment effect (reductions in odds) with the associated two-sided 95% confidence interval at Month 8 will be provided. As supportive analysis, the same model will be performed on data with no imputation for missing data in NYHA class change due to death.

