9.3.4.3 NYHA classification change over time

For categorical analysis in NYHA class change from baseline at month 8 or over time, missing NYHA classification due to death will be imputed as NYHA class worsened.

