9.3.4.4 Other variables

For the variables other than those mentioned above, double blind post-baseline LOCF will be utilized for imputing missing data unless specific rules are mentioned in the analysis sections. If it deems necessary, multiple imputations method may be used in addition to the available data analysis for each variable when the missing at random assumption is considered reasonable.

10 Safety evaluation

Safety will always be evaluated based on the VRS and LRS for run-in phase and the SAF for double-blind phase. Note that, in general, SAF is a subset of LRS and LRS is a subset of VRS.

The safety evaluation will include:

- Specific identified and potential risk and safety factors evaluation
- Adverse events
- Laboratory evaluations
- Vital signs
- Electrocardiogram

The following subgroups will be evaluated for safety, except for the specific identified and potential risk analysis:

- Age group <65, ≥65 years
- Age group <75, ≥75 years
- Gender (male, female)
- Race (Caucasian, Black, Asian, Other)
- Region

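### Read literally, the clinical composite scores non-CV deaths without a prior HF hospitalization, and patients with no assessments and no major AE, as Unchanged

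*SAP*

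**What the plan says.** SAP 9.3.3.3 builds the composite at a selected visit from NYHA class, the patient global assessment and major adverse events.

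- Worsened has three routes: "Worsened, if i) NYHA class increases at the selected visit; or ii) Global Assessment is worse at the selected visit; or iii) experiences a major". The quote stops just short of the end; the third route is a major adverse event at any time until that visit.
- The events are then limited: "Major AEs are adjudication-confirmed CV death and heart failure hospitalizations".
- Improved needs a gain on one component, no loss on the other, and no major event.
- The third class is whatever remains: "Unchanged, if neither" Improved nor Worsened applies. It does not require the patient to be alive or either component to be observed.

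The same section says of the analysis: "The analysis will be based on all available data in the FAS and likelihood method with an assumption of missing at random for missing data".

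Protocol 6.6.2 describes the composite as NYHA class and global assessment "combined with the occurrence of major adverse clinical events as defined by CV death and hospitalization for HF". It gives no rule for non-CV death or for a missing component.

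Elsewhere the SAP does say what happens after death, without regard to cause:

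- SAP 9.3.2.3 (NYHA at Month 8): "The NYHA class change after patients who have died will be categorized into" the worsened class.
- SAP 9.3.4.3 (NYHA over time): "missing NYHA classification due to death will be imputed as NYHA class worsened".
- SAP 9.3.2.2 and 9.3.4.2 (KCCQ clinical summary score): a score of 0 at all scheduled visits after death.

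For variables without their own rule, SAP 9.3.4.4 says that "double blind post-baseline LOCF will be utilized for imputing missing data unless specific rules are mentioned in the analysis sections".

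**The concern.** A residual class absorbs everyone who does not meet the other two definitions. A patient dead of a non-CV cause has no NYHA class or global assessment at later visits and has not had a major event as the SAP defines it, unless there was an earlier HF hospitalization. Deaths of unknown cause, which SAP 9.3.1.2 lists apart from CV death, fall into the same gap unless they are adjudicated as CV. Such patients would sit in the middle of an ordinal scale on which death should be at the bottom. The affected group grows with follow-up, and the composite is analysed at Month 8 and at 1, 2 and 3 years.

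A catch-all class also leaves nobody missing, so the missing-at-random sentence has nothing to act on unless missingness is defined first. Two programmers working from this text could produce different datasets.

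**Working it through.** The plan states no power or sample size for this composite, so there is no figure of its own to reproduce. The check has two parts: the literal rule, and the number of patients it could touch.

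**1. The rule with a component missing.** NYHA can be lower, same, higher or missing. The global assessment can be improved, unchanged, worse or missing. At least one is missing in 3 + 3 + 1 = 7 patterns, and with or without a major event this gives 7 × 2 = 14 cases. A condition on a missing component is taken as not met.

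- Major event present: all 7 are Worsened.
- No major event, but NYHA higher with global missing, or NYHA missing with global worse: 2 are Worsened.
- No major event, remaining patterns: 5 are Unchanged. These are NYHA lower/global missing; NYHA same/global missing; NYHA missing/global improved; NYHA missing/global unchanged; both missing.

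The total is 9 Worsened and 5 Unchanged. Two of the five (NYHA lower/global missing, and NYHA missing/global improved) would become Improved if a missing component were taken as not worse. The text does not say which.

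**2. One patient, several rules.** Take a non-CV death with no earlier HF hospitalization, at a visit after death.

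| Rule | Result |
|---|---|
| Residual class, SAP 9.3.3.3 | Unchanged |
| Available-data/MAR sentence, SAP 9.3.3.3 | Missing |
| NYHA death rule, SAP 9.3.4.3, if carried into the composite | Worsened |
| LOCF default, SAP 9.3.4.4, if the MAR sentence is not a specific rule | Last value |

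**3. Number of non-CV deaths.** Inputs: N = 4600 and CV mortality 4% per year (SAP 13.1); all-cause mortality 5% per year (SAP 13.3.4); Month 8 = Week 32 (SAP 9.2).

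Check on the mortality inputs: 0.04 × 1.25 = 0.05. With 5% per year in the control arm and 3.375 years of follow-up, expected deaths are 2300 × [(1 − exp(−0.05 × 3.375)) + (1 − exp(−0.05 × HR × 3.375))]. This gives 648 for HR 0.80 and 664 for HR 0.85. Power = Φ(½√deaths × |ln HR| − 1.96) is then 0.81 and 0.55, against the stated 81% and 56%. The inputs are therefore read as intended.

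The implied non-CV rate is 5% − 4% = 1% per year. With constant competing hazards, non-CV deaths by time t = 4600 × (0.01/0.05) × (1 − exp(−0.05t)) = 920 × (1 − exp(−0.05t)).

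- Week 32 (t = 32 × 7/365.25 = 0.613): 28 (0.6%)
- 1 year: 45 (1.0%)
- 2 years: 88 (1.9%)
- 3 years: 128 (2.8%)

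If non-CV mortality were 2% per year (an assumption), the counts are 55 at Week 32 and 253 (5.5%) at 3 years. At an assumed 3% they are 83 (1.8%) and 373 (8.1%).

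These counts include patients with an earlier HF hospitalization, who are already Worsened and must be subtracted. The documents do not give that overlap.

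**4. Missing by schedule.** The model uses all post-randomization visits. Protocol 6.6.2 has NYHA assessed at every visit, but Protocol Table 6-1 does not schedule the global assessment at Week 4. There the component is absent by design, so the rule for a missing component matters beyond dropout.

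**The case against.** The strongest reply is that the SAP nowhere says unassessed patients are Unchanged. The composite is defined from assessments at a selected visit, and the same section says available data are used with missing values assumed missing at random. On that reading an unassessed patient is simply missing, and LOCF gives way because the section has its own rule. For deaths, SAP 9.3.4.3 sits under general missing-data handling and covers NYHA missing due to death from any cause. Carried into the first Worsened criterion, it would make a non-CV death Worsened. Much of this stands for missing assessments, where the likely intention can be inferred and the defect is one of drafting. It is weaker for deaths: the NYHA rule does not name the composite and the composite section does not cite it. Treating a death as missing at random would also depart from the SAP's handling of NYHA and KCCQ.

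A reader might infer something stronger: that every non-CV death and every patient lacking NYHA or global assessment is scored Unchanged, so that about 10% of patients (4600 × 0.10 = 460) default to the middle class and treatment differences shrink by about a tenth. The documents do not support this. An earlier HF hospitalization, or one observed worsening component, already gives Worsened. The 10% in SAP 13.3.1 concerns patients with no KCCQ assessment, who are excluded from that analysis. The KCCQ has a translation exemption, and Protocol 6.6.2 states none for the global assessment.

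It can also be said that counting all deaths alters an endpoint whose events the protocol defines as CV death and HF hospitalization (Protocol 2.3 and 6.6.2). That is true, and the change should be declared.

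**Conclusion.** The point holds as a low-impact correction. For non-CV deaths without a prior HF hospitalization, the rule as written gives Unchanged, at odds with the SAP's own NYHA and KCCQ conventions. For patients with no assessments and no major event, the residual class and the missing-at-random sentence contradict each other, which alone would call only for clarification.

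The deaths affected are at most about 28 by Week 32 and 128 by year 3. This assumes 1% per year non-CV and 4% per year CV mortality, constant hazards, and the same rates in both arms. The year-3 figure applies the risk to all 4600 patients. With a planned minimum follow-up of 2 years 2 months, fewer will reach that visit. The effect on the cumulative odds ratio is not estimated, because the documents give no expected category distribution. The endpoint is exploratory, with no multiplicity adjustment, and the primary and secondary analyses are untouched.

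**What to change.** In the composite derivation in SAP 9.3.3.3:

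1. Class death from any cause up to the visit as Worsened, in line with SAP 9.3.2.3 and 9.3.4.3. State that this departs slightly from the protocol's CV-death wording.
2. Assign Improved or Unchanged only when both NYHA and the global assessment are observed at that visit.
3. Otherwise set the composite to missing, under the stated missing-at-random model, unless a worsening criterion is met.

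The cost is a few lines of text and programming, settled before unblinding. Data collection and alpha do not change.

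There is one downside. Keeping partly observed patients only when they are Worsened makes missingness depend on outcome. The effect is slight where both components are scheduled. At Week 4, where the global assessment is not scheduled, the observed composites would be almost all Worsened. A sensitivity analysis limited to visits where both components are scheduled is advisable, and the sponsor could reasonably make that restriction part of the main analysis.

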9.3.3.4 Analysis of count data

Count data include:

- Number of HF events;
- Number of worsening HF events or CV deaths;
- Number of hospital admissions;
- Number of days/stays in ICU;
- Number of stays in ICU;
- Number of re-hospitalizations;
- Number of ER visits for HF;
- Number of 30 day hospital readmissions (after a prior in-study HF hospitalization).

Count variables will be analyzed using a negative binomial model ([McCullagh and Nelder 1989](#)) with the count data as the dependent variable and treatment group and region as fixed-effect factors and log(follow-up duration) as the off-set. The model estimated event rates (intensities/risk rate) and their 95% confidence intervals will be provided by treatment group. The treatment comparison will be performed through the estimated ratio of risk rates. The estimated reduction in event rate (ratio LCZ696/valsartan) and its 95% confidence interval will also be provided. Note that, in case when the follow-up durations depend on the treatments (potentially informative censorings), the estimated rate reduction should be interpreted with caution. However, when LCZ696 has a reduction in mortality, the rate reduction estimated from the negative binomial model will become conservative. As mentioned before, for 30 day hospital readmission, the analysis set will be restricted to patients who had hospitalization for HF at least once during double blind period. This implies that the baseline treatment group balance obtained from the randomization may be broken.

Descriptive statistics (n, mean, standard deviation, median, max, and min) will be provided for these variables by treatment group. For each variable, the annualized count for each patient is calculated as the total counts during the study divided by the total duration of the double blind

treatment phase, multiplied by 365.25. The annualized counts will be summarized according to treatment groups.

9.3.3.5 Subgroup analysis

Subgroup of ACEI intolerant patients

The primary and secondary variables as well as the symptom based variables, such as the clinical composite assessment, and so on, will also be analyzed using methods proposed above for the sub-group of ACEI intolerant patients.

Subgroup analysis for exploratory analysis

Subgroup analysis for the exploratory objectives will be performed for change in MMSE total score from baseline and the EQ-5D assessments for Region (North America, Western Europe, Central Europe, and the United Kingdom), age group, diabetes, AF, NT proBNP (<median or > median), and use of aldo antagonist at baseline.

9.3.4 General handling of missing data in the efficacy analyses

9.3.4.1 Time to event variables

For time-to-event variables, the censoring rules are presented in [Section 9.2](#).

9.3.4.2 KCCQ clinical summary score

The clinical summary score is a mean of the physical limitation and total symptom scores. The total symptom score is the mean of the symptom frequency and symptom burden scores. Each scale score (the physical limitation, symptom frequency or symptom burden) is calculated as the mean of its item scores and transformed to a 0–100 scale, with higher score indicating higher level of functioning. A score of 100 represents perfect health whereas a score of 0 represents dead. For patients who die, a worst score (score of 0) will be imputed for the clinical summary score at all subsequent scheduled visits after the date of death where the clinical summary score would have been assessed.

9.3.4.3 NYHA classification change over time

For categorical analysis in NYHA class change from baseline at month 8 or over time, missing NYHA classification due to death will be imputed as NYHA class worsened.

9.3.4.4 Other variables

For the variables other than those mentioned above, double blind post-baseline LOCF will be utilized for imputing missing data unless specific rules are mentioned in the analysis sections. If it deems necessary, multiple imputations method may be used in addition to the available data analysis for each variable when the missing at random assumption is considered reasonable.

10 Safety evaluation

Safety will always be evaluated based on the VRS and LRS for run-in phase and the SAF for double-blind phase. Note that, in general, SAF is a subset of LRS and LRS is a subset of VRS.

The safety evaluation will include:

- Specific identified and potential risk and safety factors evaluation
- Adverse events
- Laboratory evaluations
- Vital signs
- Electrocardiogram

The following subgroups will be evaluated for safety, except for the specific identified and potential risk analysis:

- Age group <65, ≥65 years
- Age group <75, ≥75 years
- Gender (male, female)
- Race (Caucasian, Black, Asian, Other)
- Region

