For the rate change in eGFR, the eGFR slope will be estimated from a repeated measures ANCOVA model including treatment, region, time (when the eGFR is assessed in months), and treatment-by-time as fixed effects with random intercept and slope (time) and a common unstructured covariance. The least-squared means of slopes for within and between treatment groups, and the corresponding two-sided 95% confidence intervals will be provided.

Changes from randomized treatment epoch baseline in KCCQ scores, similarly for changes from baseline in EQ-5D VAS and EQ-5D index, will be analyzed based on a repeated measures ANCOVA model in which treatment, region, visit, and treatment-by-visit interaction will be included as fixed-effect factors and baseline value as a covariate, with a common unstructured covariance matrix among visits for each treatment group. Treatment comparisons and effect size estimates at different visits will be provided. The analysis will be performed based on all available data up to 3 years in the FAS and based on likelihood method with an assumption of missing at random for missing data.

KCCQ score obtained at the beginning of treatment run-in epoch is used as the run-in baseline and the analysis of KCCQ changes using a repeated measures ANCOVA model as described above will be repeated again using run-in baseline.

For pre-selected biomarkers, change from baseline to a pre-defined time-point (Week 4 and Month 8) in logarithmic scale will be analyzed using a similar repeated measures ANCOVA model as described above.

For days alive out of the hospital during the first 12 months, it will be treated as a continuous variable. The mean difference between treatment groups will be compared using an ANCOVA model with factors of region and treatment group. Days alive out of the hospital during the study duration will be similarly analyzed as appropriate.

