- Rate of change in eGFR (eGFR slope);
- Time from randomization to new onset diabetes mellitus (NODM);
- Time to new onset of atrial fibrillation (AF);
- Number of days staying in intensive care unit (ICU), number of stays in intensive care unit (ICU), number of re-hospitalizations for HF, and number of ER visits for HF;
- Indicator of 30 day HF rehospitalization (after a prior HF hospitalization during double blind phase);
- Number of rehospitalizations within 30 days after discharge;
- Time between HF hospital readmissions;
- Changes in pre-specified biomarkers (e.g., cardiac, vascular, renal, collagen, metabolism, and inflammatory biomarkers) from baseline to predefined time-points (in a subset of patients);
- Variables to characterize the PK of valsartan, AHU377, and LBQ657 at steady-state in patients receiving LCZ696 using population modeling and/or non-compartmental based methods;
- Change from baseline in Mini-Mental State Examination (MMSE) summary score at year 2 (week 96).

Among the variables above, some of them or their components need to be adjudicated to confirm the reported types and occurrences based on the unified criteria for analyses. The adjudication of these events is based on an adjudication process through an independent Endpoint Adjudication Committee. The following events will be assessed by the Endpoint Adjudication Committee during the study:

- All death events;
- Unplanned hospitalization for HF;
- MI;
- Stroke;
- Renal dysfunction (including occurrence of end stage renal disease);
- Others (new onset atrial fibrillation (NOAF), NODM)

In the analysis, as specified before, only adjudicated events will be utilized if the events included in the analysis are required to be adjudicated. However, in the sensitivity analysis, the investigator reported events may also be used.

As specified before, all events and endpoints occurred or measured prior to or at the specified analysis time-points (such as Month 8, Month 12, etc.), including the analysis cut-off date, will be counted, unless otherwise specified.

Censoring variables:

Number of events and time-to-event variable are usually subject to censoring. The censoring can be caused by withdrawal of consent, lost to follow-up, other competing events, or administrative reasons (interim or analysis cutoff date). Below are the rules for deriving censoring variables in the analyses (primary, secondary, exploratory):

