9.3.3.2 Analysis of continuous variables

Continuous variables, which can be analyzed using the linear models with or without transformation on the responses, are:

- Rate of change (slope) in eGFR from baseline to endpoint;
- Changes in health-related quality of life (assessed by clinical summary score, total score and individual scores of the sub-domains from the KCCQ and scores of the EQ-5D for health status (EQ-5D index derived from EQ-5D descriptive system and EQ-5D VAS) from baseline to pre-defined time-points;
- Changes (in log-scale when skewed) from baseline to pre-defined time-points in pre-selected biomarkers (e.g., cardiac, vascular, renal, collagen, metabolism, and inflammatory biomarkers);
- Summarize pharmacokinetics (PK) parameters at steady-state using population modelling;
- Days alive out of the hospital during the first 12 months (48 weeks), and during the entire double-blind period;
- Change from baseline in MMSE summary score at year 2 (week 96).

Analysis for rate of change (slope) in eGFR

For the rate change in eGFR, the eGFR slope will be estimated from a repeated measures ANCOVA model including treatment, region, time (when the eGFR is assessed in months), and treatment-by-time as fixed effects with random intercept and slope (time) and a common unstructured covariance. The least-squared means of slopes for within and between treatment groups, and the corresponding two-sided 95% confidence intervals will be provided.

Analysis of changes in health-related quality of life change

Changes from baseline in KCCQ mean scores (for all 10 scores), similarly for changes from baseline in EQ-5D VAS and EQ-5D index (if available), will be analyzed based on a repeated measures ANCOVA model in which treatment, region, visit, and treatment-by-visit interaction will be included as fixed-effect factors and baseline value as a covariate, with a common unstructured covariance matrix among visits for each treatment group. Treatment comparisons and effect size estimates, including two-sided 95% confidence intervals, at different visits will be provided. The analysis will be performed based on all available data up to 3 years in the FAS and based on likelihood method with an assumption of missing at random (MAR) for missing data.

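### Read literally, the SAP's LOCF default applies to the exploratory eGFR slope, where it flattens the decline; the slope analysis needs its own observed-data rule

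*SAP*

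**What the plan says.** SAP 9.3.4 is headed "General handling of missing data in the efficacy analyses". Its first three subsections cover time-to-event variables, the KCCQ clinical summary score and NYHA class. Section 9.3.4.4 then covers everything else: "For the variables other than those mentioned above, double blind post-baseline LOCF will be utilized for imputing missing data unless specific rules are mentioned", meaning rules given where each analysis is described. The sentence after that adds that, if needed, a "multiple imputations method may be used in addition to the available data analysis for each variable" when missing at random is thought reasonable.

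The eGFR slope is listed among the exploratory variables in SAP 9.2. Its analysis paragraph in SAP 9.3.3.2 specifies a repeated measures model with "treatment-by-time as fixed effects with random intercept and slope (time) and a common" unstructured covariance. It says which estimates and intervals will be given, and nothing about missing values. Protocol 9.5.2 has the same model and the same silence.

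Neighbouring analyses do state a rule. KCCQ and EQ-5D (SAP 9.3.3.2), NYHA (9.3.2.3), MMSE (9.3.3.2) and the repeated ordinal variables (9.3.3.3) each specify available data, likelihood and missing at random.

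**The concern.** The escape clause in 9.3.4.4 works only where an analysis section gives its own rule. The eGFR-slope paragraph gives none, so a programmer following the SAP would carry the last double-blind value forward. The text does not say where this stops, so scheduled visits after a patient's death could be filled as well.

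A run of identical values after the last measurement is a segment of zero slope. In a declining population it pulls the estimated decline toward zero in the arm concerned. The pull grows with the amount of loss, so arms with different loss are distorted by different amounts. The filled values also count as data, which can make the estimate look more precise than it is. The model specified needs no imputation, because it accepts patients with different numbers of visits.

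At stake is one protocol objective, slowing the decline in eGFR, tested at two-sided 0.05 without multiplicity adjustment.

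**Working it through.** **Plan's own figures.** The documents give no eGFR slope, standard deviation or LOCF effect, so there is none to reproduce. The input borrowed from them is mortality: 5% per year over an average of 3.375 years (SAP 13.3.4). That input can be checked against the stated power.

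- Deaths with a 20% reduction: 2300 × (1 − e^(−0.05×3.375)) + 2300 × (1 − e^(−0.04×3.375)) = 2300 × (0.155 + 0.126) ≈ 648.
- Power: Φ(½ × √648 × |ln 0.80| − 1.96) = Φ(0.88) = 0.81. The SAP states 81%.
- With a 15% reduction, 664 deaths give 0.554. The SAP states 56%.

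At 5% per year, 1 − e^(−0.16875) = 15.5% of patients die within 3.375 years.

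**Simulation inputs.**
- From the documents: 4600 patients, 1:1; eGFR at weeks 0, 4, 16, 32 and 48, then every 24 weeks (Protocol Table 6-1); follow-up uniform from 2.17 to 4.59 years (SAP section 4: 2.17 minimum plus 2.42 enrolment); loss of 5% per year (mortality).
- Assumed: true slopes in mL/min/1.73 m² per year; SDs of 18 (intercept), 2 (slope) and 6 (residual); loss above 5% per year; loss independent of a patient's own slope; carry-forward to the end of each patient's potential follow-up.
- Model: random intercept and slope with treatment-by-time, maximum likelihood, region omitted. It was fitted once to available data and once after LOCF. Scenario A is the mean of three replicates; the others are single replicates.

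| Scenario (loss per year; true control / active slope) | Values imputed | Available data: control / active; difference (SE) | LOCF: control / active; difference (SE) |
|---|---|---|---|
| A: 5% both; −2.5 / −2.0 | 6.4% | −2.494 / −1.959; 0.535 (0.086) | −2.302 / −1.810; 0.493 (0.082) |
| B: 10% both; −2.5 / −2.0 | 12.0% | −2.496 / −2.067; 0.429 (0.089) | −2.142 / −1.768; 0.373 (0.081) |
| C: 15% both; −2.5 / −2.0 | 17.2% | −2.500 / −2.043; 0.457 (0.077) | −1.971 / −1.612; 0.359 (0.082) |
| D: 10% control, 5% active; −2.5 / −2.5 | 9.0% | −2.496 / −2.570; −0.074 (0.087) | −2.141 / −2.383; −0.242 (0.082) |
| E: 5% both; −4 / −3 | 6.2% | −3.997 / −3.070; 0.927 (0.084) | −3.684 / −2.845; 0.839 (0.083) |

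**Within-arm flattening (control), 1 − LOCF/available.**
- A: 1 − 2.302/2.494 = 7.7%
- B: 1 − 2.142/2.496 = 14.2%
- C: 1 − 1.971/2.500 = 21.2%
- E: 1 − 3.684/3.997 = 7.8%

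A further four-replicate run at 5% per year gave −2.50 against −2.31 (7.6%), and two further replicates also gave about 8%.

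**Arm difference, equal loss of 5% per year.** In A it fell from 0.535 to 0.493. The other runs gave 0.469 to 0.457, 0.484 to 0.443 and 0.608 to 0.557. In the last two, z moved from 5.61 to 5.37 and from 7.20 to 6.91.

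**Standard error.** In A it fell by 1 − 0.082/0.086 = 4.7%, and the further runs at those slopes gave 4.5% to 4.7%. It is not uniform: E fell by about 1%, and the single replicate of C rose.

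**Unequal loss.** In D, with no true difference, LOCF moved the estimate by −0.242 − (−0.074) = −0.168, about two standard errors, against the arm with less loss. The plan's own mortality contrast is milder: 5% against 4% per year under a 20% reduction. Scaling A in proportion, flattening would be 7.7% against 7.7% × 4/5 = 6.2%, a shift of about 2.5 × (0.077 − 0.062) ≈ 0.04, or half a standard error.

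**The case against.** The best reply is that LOCF was never meant for this model. The SAP says "the eGFR slope will be estimated from a repeated measures ANCOVA model including treatment, region, time (when the eGFR is assessed in months", and a carried-forward value has no assessment time. The same section describes multiple imputation as an addition to an available-data analysis, which implies that such an analysis is the base. A random-slope model is the usual choice when values are left missing. No document says that values are created after death.

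This is good evidence of intent, and it stands as such. It does not exempt the slope: the LOCF sentence is worded as an instruction, its only exception is a stated rule, and the slope paragraph has none. Two programmers could each defend a different analysis from the same text.

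It is also fair that the inference barely moves at the documented mortality with equal loss, and that larger effects need assumed loss. The good recovery by the available-data fit partly reflects how loss was simulated. If steep decline itself leads to death in ways the observed values do not capture, that fit can be biased too.

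A reader might infer that the biomarker and patient global assessment analyses also fall to LOCF. The documents do not support that. The biomarker model is described by reference to the repeated measures model above it, which carries the available-data rule. The global assessment is to be handled similarly to the ordinal variables, directly after their available-data and missing-at-random sentence. Both more naturally inherit that rule.

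**Conclusion.** Wrong as written, for one exploratory variable. Taken at its word, the SAP applies LOCF to the eGFR slope with no stop at death, and it contradicts its own reference to an available-data analysis.

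Under steady decline the within-arm slope is flattened by about 8% at the plan's 5% annual mortality, rising to 14% and 21% at assumed losses of 10% and 15% per year. At 5% per year, equal in both arms and with slopes of −2.5 and −2.0, the arm difference is slightly attenuated and its standard error is about 5% too small. When loss differs by arm a spurious difference can arise. Its direction depends on which arm loses more patients, so LOCF cannot be called conservative here. The direction of the within-arm bias follows from steady decline; the sizes rest on assumed slopes and SDs.

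A reader might take this as a threat to the trial's renal conclusions. It is not: the secondary renal composite is a time-to-event endpoint analysed by a Cox model with its own censoring rules. The primary endpoint and the other secondary endpoints also have their own methods.

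**What to change.** In SAP 9.3.3.2, state that the eGFR slope is estimated from observed values only, by likelihood under missing at random in the random intercept-and-slope model already specified, with no LOCF and no values imputed after death. In SAP 9.3.4.4, remove the LOCF default or restrict it to named variables, so that it no longer conflicts with the sentence that follows it.

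Optionally, add one line confirming that the biomarker and patient global assessment analyses use the available-data likelihood rule that they reference. A sensitivity analysis for informative death or dropout, such as a joint model of slope and survival, would address the limit of the missing-at-random fit.

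The required changes are SAP wording. They need no new data and less programming than LOCF. The optional joint model would need some programming.
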